4.2.2. Other Secondary Objectives

These are prespecified objectives that will not be adjusted for multiplicity.

Objectives	Endpoints
To test the hypothesis that baricitinib 1-mg QD, 2-mg QD, or 4-mg QD is superior to placebo in the treatment of patients with moderate to severe AD.	
 • Proportion of patients achieving IGA of 0 or 1 with a ≥ 2-point improvement at Week 4
To compare the efficacy of baricitinib 1-mg QD, 2-mg QD, or 4-mg QD to placebo in AD during the 16-week double-blind placebo-controlled period as measured by physician-assessed signs and symptoms of AD.	
 • Proportion of patients achieving EASI50 at 16 weeks • Proportion of patients achieving IGA of 0 at 16 weeks • Mean change from baseline in SCORAD at 16 weeks • Proportion of patients achieving SCORAD90 at 16 weeks • Mean change from baseline in BSA affected at 16 weeks • Proportion of patients developing skin infections requiring antibiotic treatment by Week 16
To compare the efficacy of baricitinib 1-mg QD, 2-mg QD, or 4-mg QD to placebo in AD during the 16-week, double-blind, placebo-controlled treatment period as assessed by patient-reported outcome/QoL measures.	
 • Percent change from baseline in Itch NRS at 1 week and 16 weeks • Mean change from baseline in Itch NRS at 4 weeks and 16 weeks • Mean change from baseline in the total score of the POEM at 16 weeks • Mean change in the PGI-S-AD scores at 16 weeks • Mean change from baseline in HADS at 16 weeks • Mean change in the DLQI scores at 16 weeks • Mean change in the WPAI scores at 16 weeks • Mean change in the EQ-5D-5L scores at 16 weeks

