6.2.4. Derived Data

- Age (year), derived using first dose date as the reference start date and July 1st of birth year and truncated to a whole-year (integer) age. Patients whose derived age is less than 18 will have the required minimum age of 18 at informed confirmed; reporting for age, age groups, and lab ranges, however will be based on their derived age.
- Age group (<65, ≥65 years old)
- Age group (<65, ≥65 to <75, ≥75 to <85, ≥85 years old)
- Body mass index (BMI) (kg/m^2) = $\text{Weight (kg)} / ((\text{Height (cm)} / 100)^2)$
- BMI category (<25 kg/m^2 , ≥25 to <30 kg/m^2 , ≥30 kg/m^2)
- The duration of AD from diagnosis (years) = $[(\text{Date of informed consent} - \text{Date of AD diagnosis}) + 1] / 365.25$.
 - If year of onset is missing, duration of AD will be set as missing. Otherwise, unknown month will be taken as January, and unknown day will be taken as 01. The duration of AD will be rounded to 1 decimal place.
- Duration of AD (years) category (0 to <2 years, 2 to <5 years, 5 to <10 years, 10 to <20 years, ≥20 years)
- Diagnosis age (years), derived using diagnosis date as the reference start date and July 1st of birth year and truncated to a whole-integer age.
- Diagnosis age group (<18, ≥18 to <50, ≥50 years old)
- Change from baseline = postbaseline measurement at Visit x – baseline measurement.
 - If a baseline value is missing, it will not be imputed and the change from baseline will not be calculated.
- Percent change from baseline at Visit x:
 $((\text{Post-baseline measurement at Visit x} - \text{Baseline measurement}) / \text{Baseline measurement}) * 100$.
 - If a baseline value is missing, it will not be imputed and percent change from baseline will not be calculated.
- Weight (kg) = weight (lbs) * 0.454.
- Weight category (<60 kg, ≥60 to <100 kg, ≥100 kg)
- Height (cm) = height (in) * 2.54.
- Cyclosporine inadequate efficacy (yes, no)
 - Set **yes** if the reason for discontinuation is inadequate response.
- Cyclosporine intolerance (yes, no)

- Set **yes** if the reasons for discontinuation are: intolerance to medication or contraindication (Physician indicated cyclosporine was used and a contraindication was noted).
- Cyclosporine contraindication [ineligible] (yes, no)
 - Set to **yes** if cyclosporine never used because of a contraindication
- Cyclosporine inadvisable (yes, no)
 - Set to **yes** if the following reasons were selected for either not using the medication or discontinuing the medication:

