Work Productivity and Activity Impairment: Atopic Dermatitis (WPAI-AD)	The Work Productivity and Activity Impairment Questionnaire–Atopic Dermatitis (WPAI-AD) records impairment due to AD during the past 7 days. The WPAI-AD consists of 6 items grouped into 4 domains: absenteeism (work time missed), presenteeism (impairment at work/reduced on-the-job effectiveness), work productivity loss (overall work impairment/absenteeism plus presenteeism), and activity impairment. Scores are calculated as impairment percentages (Reilly et al. 1993), with higher scores indicating greater impairment and less productivity.	Employment status	Question (Q)1	Single item, missing if missing.
		Change in employment status	Employed at baseline and remained employed: Q1 = 1 at post-baseline visit and at baseline visit. Not employed at baseline and remain unemployed: Q1 = 0 at post-baseline visit and at baseline visit.	Missing if baseline or observed value is missing.
		Percentage of absenteeism	Percent work time missed due to problem: $(Q2/(Q2 + Q4))*100$	If Q2 or Q4 is missing, then missing.
		Change from baseline in absenteeism	Change from baseline: observed absenteeism – baseline absenteeism	Missing if baseline or observed value is missing.
		Percentage of presenteeism	Percent impairment (reduced productivity while at work) while working due to problem: $(Q5/10)*100$	If Q5 is missing, then missing.
		Change from baseline in presenteeism	Change from baseline: observed presenteeism – baseline absenteeism	Missing if baseline or observed value is missing.
		Overall work impairment	Percent overall work impairment (combines absenteeism and presenteeism) due to problem: $(Q2/(Q2+Q4) + [(1-Q2/(Q2+Q4))*(Q5/10)])*100$	If Q2, Q4, or Q5 is missing, then missing.

Measure	Description	Variable	Derivation / Comment	Imputation Approach if Missing Components
		Change from baseline in work impairment	Change from baseline: observed work impairment – baseline work impairment	Missing if baseline or observed value is missing.
		Percentage of impairment in activities	Percent activity impairment (performed outside of work) due to problem: $(Q6/10)*100$	If Q6 is missing, then missing.
		Change from baseline in impairment in activities	Change from baseline: observed impairment in activities – baseline impairment in activities	Missing if baseline or observed value is missing.

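### WPAI overall work impairment is set to missing when Q5 is blank, even where the SAP's own formula fixes the score at 100% without Q5

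*SAP*

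**What the plan says.** Table JAHM.6.6 derives three work-related WPAI-AD scores from items Q2, Q4 and Q5.

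- **Absenteeism** is described as "Percent work time missed due to problem" and computed as Q2/(Q2 + Q4) × 100. Its missing-component rule is "If Q2 or Q4 is missing, then missing". Q5 plays no part.
- **Presenteeism** is Q5/10 × 100, described as "Percent impairment (reduced productivity while at work) while working due to problem".
- **Overall work impairment** combines the two. After its opening bracket the derivation reads "Q2/(Q2+Q4) + [(1-Q2/(Q2+Q4))*(Q5/10)])*100", and its missing-component rule is "If Q2, Q4, or Q5 is missing, then missing". No exception is given for a patient who worked no hours.

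Scores are percentages, "with higher scores indicating greater impairment and less productivity", so 100% is the worst possible value.

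Section 4.2.2 lists "Mean change in the WPAI scores at 16 weeks" among the secondary objectives that are not adjusted for multiplicity. Table JAHM.6.7 analyses the score and its change from baseline at Week 16 by MMRM, with ANCOVA on mLOCF data as sensitivity analysis. On baseline, Section 6.2.4 says: "If a baseline value is missing, it will not be imputed and the change from baseline will not be calculated".

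**The concern.** The formula and the missing-data rule in the same table row do not fit together. The rule treats Q5 as always necessary. The formula does not need it when no hours were worked, and that is the situation in which a question about productivity at work has nothing to refer to.

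When the rule operates for this reason, the discarded value is always the scale maximum, so the loss depends on the outcome itself.

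- **At Week 16**, the MMRM handles the worst value as missing at random (Section 6.4.2), an assumption that fits poorly when the value is what makes the item inapplicable. Under mLOCF (Section 6.4.3) an earlier post-baseline value replaces it. That value cannot exceed 100%, so it equals or understates the true score.
- **At baseline**, a patient who goes from fully off work to back at work can lose the change score.

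Absenteeism and overall impairment, two scores from one questionnaire, would then rest on different patients.

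**Working it through.** The SAP states no figure on this point, so there is none to reproduce. The check is algebra on the printed formula, followed by an illustration on assumed inputs.

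**1. The formula when no hours were worked.** Write a = Q2/(Q2 + Q4), so that overall work impairment = 100 × [a + (1 − a) × Q5/10]. The absenteeism row implies that Q2 is time missed because of AD and Q4 is time worked. With Q4 = 0 and Q2 > 0, a = Q2/Q2 = 1 and 1 − a = 0, so the score is 100 × [1 + 0 × Q5/10] = 100.

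| Q2 | Q4 | Score at Q5 = 0 | Score at Q5 = 10 |
|---|---|---|---|
| 1 | 0 | 100% | 100% |
| 8 | 0 | 100% | 100% |
| 40 | 0 | 100% | 100% |
| 39 | 1 | 97.5% | 100% |
| 20 | 20 | 50% | 100% |
| 0 | 0 | undefined (0/0) | undefined (0/0) |

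Q5 is irrelevant when Q4 = 0 and Q2 > 0. Once Q4 > 0 it matters, and setting the score to missing without it is sound. The last row is a separate gap: the printed rule does not cover it.

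**2. Can Q5 be blank?** For HADS, DLQI and the EQ-5D-5L index scores, Table JAHM.6.6 says that partial assessments cannot be saved. The WPAI rows carry no such statement and set item-level missing rules instead, so the SAP itself allows for blank WPAI items. It does not print the question wording or any skip instruction.

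**3. Illustrative effect on the mean at one visit.** Every input here is an assumption. Let a share f of employed patients be at 100% with Q5 blank, and let the others average m. The true mean is (1 − f)m + 100f and the observed mean is m, so the shortfall is f(100 − m).

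- f = 1%, m = 50: 0.01 × 50 = 0.5 points.
- f = 10%, m = 30: 0.10 × 70 = 7.0 points.

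For counts, assume 60% are employed: 0.6 × 120 = 72 per baricitinib arm and 0.6 × 240 = 144 on placebo. With f from 1% to 10%, that is about 1 to 7 patients per baricitinib arm and about 1 to 14 on placebo.

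**4. Illustrative effect on the treatment difference.** This compares simple observed means; it is not an MMRM.

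- *Unequal shares.* With 5% affected on placebo, 1% on baricitinib and m = 30 in both arms, the true means are 0.95 × 30 + 5 = 33.5 and 0.99 × 30 + 1 = 30.7. The true difference is −2.8 and the observed difference is 0.
- *Equal shares.* With the same f in both arms, the true difference is (1 − f) times the observed one. At f = 5% the observed difference is too large by a factor of 1/0.95 = 1.05.

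The direction of any bias in the treatment comparison therefore depends on inputs that the SAP does not contain.

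**The case against.** The strongest reply is that a blank Q5 is not documented. The SAP shows no questionnaire, and a patient who worked no hours but still answered Q5 would be scored 100% and kept. This stands: the trigger is inferred from the description of Q5 as impairment while working. It does not remove the defect, because the rule as printed discards a determined value whenever the blank does occur.

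Other parts of the reply also stand and limit the point.

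- A reader might infer that only the worst scores are lost. The rule also blanks ordinary item non-response at any level of impairment.
- A reader might infer that these patients drop out of the WPAI analysis. Absenteeism and activity impairment are still scored, and after a post-baseline loss the MMRM still uses the patient's other available visits.
- Section 6.2.2 defines baseline as the last non-missing value on or before first dose. The change score is lost only if no earlier value exists.
- Section 6.4 already censors health-outcome data after rescue or permanent discontinuation of study drug. For patients censored in that way the Q5 rule changes nothing at Week 16.
- A reader might infer that the treatment effect is biased because failures on placebo are hidden. The SAP gives no rates by arm, and the shifts calculated above rest on assumed inputs.

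Finally, the SAP cites a source for WPAI scoring that cannot be consulted here, so whether that source makes the same exception is unknown. The case for the change rests on the SAP's formula alone.

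**Conclusion.** The point holds as an internal inconsistency of limited reach. For Q4 = 0 and Q2 > 0 the printed formula determines overall work impairment as 100%, and the printed rule discards that value if Q5 is blank. This follows from the SAP's text and needs no assumption. That the situation arises in practice is a reasonable inference from the definition of Q5, but not a documented fact.

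The SAP does not allow the number of patients affected, or the size or direction of bias in the treatment difference, to be calculated. The 0.5 to 7.0 points is a shift in a raw mean under assumed shares and means; it is not an estimate of bias in the endpoint. Only one WPAI score within a secondary endpoint outside the multiplicity procedure is touched, and no primary or key secondary result depends on it. It is a correction worth making because it costs almost nothing, not because a main conclusion is at risk.

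**What to change.** Replace the missing-component rule for overall work impairment in Table JAHM.6.6 with:

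*If Q2 or Q4 is missing, or Q2 + Q4 = 0, then missing. If Q4 = 0 and Q2 > 0, overall work impairment = 100% regardless of Q5. Otherwise missing if Q5 is missing.*

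Presenteeism needs no change and stays missing when Q5 is missing. The new rule changes no score where Q5 was answered and Q2 + Q4 > 0, leaves the existing handling in place where Q4 > 0, and closes the undefined case Q2 = Q4 = 0. It uses only items already collected and costs one derivation line. The sponsor should check the wording against the scoring source it cites. A count by arm and visit of patients with Q4 = 0, Q2 > 0 and Q5 blank would show whether the rule mattered.

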6.13. Bioanalytical and Pharmacokinetic/Pharmacodynamic Methods

Pharmacokinetic (PK), Pharmacodynamic (PD) and Biomarker analyses to address secondary and exploratory objectives of this study will be described by Lilly in separate PK/PD and Biomarker analysis plans.

6.14. Safety Analyses

The general methods used to summarize safety data, including the definition of baseline value are described in Section 6.2.

Safety analyses will include data before and after rescue, unless otherwise stated, and patients will be analyzed according to the investigational product to which they were randomized at Visit 2. A sensitivity approach to the safety analyses will use data censored at last dose of the study drug for patients rescued to systemic therapy. These analyses will be conducted for treatment-emergent adverse events (TEAEs), serious adverse events (SAEs), AEs leading to permanent study drug discontinuation and special topics excluding deaths and malignancies. Additional analyses may be conducted using data after rescue to systemic therapy for some safety topics such as systemic TEAEs, and SAEs. Safety analyses will take place using the safety population defined in Section 6.2.1.

Safety topics that will be addressed include the following: AEs, clinical laboratory evaluations, vital signs and physical characteristics, Columbia Suicide Severity Rating Scale (C-SSRS), the Self-Harm Supplement Form, safety in special groups and circumstances, including adverse events of special interest (AESI) (see Section 6.14.5), and investigational product interruptions.

Unless otherwise specified, by-visit summaries will include planned on-treatment visits. For tables that summarize events (such as AEs, categorical lab abnormalities, shift to maximum value), post-last dose follow-up data will be included. Follow-up data is defined as all data occurring up to 30 days (planned maximum follow-up time) after last dose of treatment including rescue, regardless of study period. Listings will include all safety data.

For selected safety assessments other than events, descriptive statistics may be presented for the last measure observed during post-treatment follow-up (up to 30 days after the last dose of treatment including rescue, regardless of study period).

6.14.1. Extent of Exposure

Duration of exposure (in days) will be calculated as follows:

- Duration of exposure to investigational product (including exposure after the initiation of rescue therapy): *date of last dose of study drug including rescue – date of first dose of study drug + 1.*

Last dose of study drug including rescue is calculated as last date on study drug. For patients discontinuing study drug or study due to the reason 'Lost to Follow-up', the duration of exposure is calculated as *date of second last visit - date of first dose of study drug + 1.*

Total patient-years (PY) of exposure to study drug will be reported for each treatment group for overall duration of exposure. Descriptive statistics will be provided for patient-days of exposure and the frequency of patients falling into different exposure ranges in addition to cumulative exposures will be summarized.

Exposure ranges will be summarized as follows:

- ≥ 28 days, ≥ 56 days, ≥ 84 days, and ≥ 112 days
- > 0 to < 28 days, ≥ 28 days to < 56 days, ≥ 56 days to < 84 days, ≥ 84 days to < 112 days, and ≥ 112 days

Overall exposure for a treatment group will be summarized in total PY which is calculated according to the following formula:

- $Exposure\ in\ PYE = \text{sum of duration of exposure in days} / 365.25$

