5.1. Summary of Study Design

Study I4V-MC-JAHM (JAHM) is a Phase 3, multicenter, randomized, double-blind, placebo-controlled, parallel-group, outpatient study evaluating the efficacy and safety of baricitinib 1-mg once daily (QD), 2-mg QD, and 4-mg QD as compared to placebo in adult patients with moderate to severe AD. The study is divided into 3 periods, a 5-week Screening period, a 16-week Double-Blinded Treatment period, and a 4-week Post-Treatment Follow-Up period. For those patients who complete the 16-week treatment period, there is an option to participate in the long-term extension study I4V-MC-JAHN (JAHN).

Approximately 600 patients ≥ 18 years of age who have responded inadequately to or who are intolerant to topical therapy will be randomized at a 2:1:1:1 ratio to receive placebo QD, baricitinib 1-mg QD, baricitinib 2-mg QD, or baricitinib 4-mg QD (240 patients in the placebo group; 120 patients in each baricitinib treatment group). Patients will be stratified at randomization according to disease severity (IGA 3 vs. 4) and geographic region.

Study JAHM will consist of 3 periods:

- Period 1: Screening period is between 8 and 35 days prior to Week 0 (Visit 2)
- Period 2: Double-Blind, Placebo-Controlled Treatment period from Week 0 (Visit 2) through Week 16 (Visit 8)
- Period 3: Post-Treatment Follow-Up period from last treatment visit at Week 16 (Visit 8) or Early Termination Visit (ETV) to approximately 28 days after the last dose of investigational product

[Figure JAHM.5.1](#) illustrates the study design. The blinding procedure is described in the Protocol.

[figure not shown]

Figure JAHM.5.1. Illustration of study design for Clinical Protocol I4V-MC-JAHM.

Abbreviations: AD = atopic dermatitis; eGFR = estimated glomerular filtration rate; PPD = purified protein derivative; QD = once daily; V = visit; W = week.

- Applicable to patients taking topical treatments (excluding emollients) or systemic treatments for AD at the time of screening.
- For patients randomized to the 4-mg once daily dose who have renal impairment (defined as eGFR <60 mL/min/1.73 m²), the baricitinib dose will be 2-mg once daily.
- Patients for whom PPD skin test for the evaluation of tuberculosis infection was performed at V1 must return and PPD test must be read 48 to 72 hours after Visit 1 (post-PPD).
- Occurs approximately 28 days after the last dose of investigational product. Not required for those patients entering the long-term extension study JAHN.

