Postbaseline measurements are collected after study drug administration through Week 16 (Visit 8) or early discontinuation visit. Efficacy data collected at scheduled visits (e.g., eCOA, ClinRO) will be used in all analyses unless it is missing. If an assessment is missing at a scheduled visit, an unscheduled post-baseline assessment can be used provided it falls within the window interval as follows: a ± 2 day window is used for Visit 3 (Week 1), Visit 4 (Week 2), and Visit 5 (Week 4); and a ± 4 day window is used to Visit 6 (Week 8), Visit 7 (Week 12), and Visit 8 (Week 16). If there is more than 1 unscheduled visit within the defined visit window and no scheduled visit assessment is available, the unscheduled visit closest to the scheduled visit date will be used. If two unscheduled visits of equal distance are available, then the latter of the two will be used.

Postbaseline daily diary endpoints will be the mean of weekly visit windows (diary windows) anchored on day of first dose (Day 1) and day of Week 16 scheduled visit. Weeks 1-14 are defined as follows:

Week	Days
1	1-7
2	8-14
3	15-21
4	22-28
5	29-35
6	36-42
7	43-49
8	50-56
9	57-63
10	64-70
11	71-77
12	78-84
13	85-91
14	92-98

The Week 16 diary window is the 7 days prior to the scheduled Week 16 visit. If there is no Week 16 scheduled visit, the 7 days prior to the last visit (whether scheduled or unscheduled)

occurring after Day 105 constitutes the Week 16 diary window if one exists. If there is no visit on which to anchor the Week 16 diary window, the Week 16 interval and its associated mean are defined as missing. If there are less than 4 non-missing assessments in the Week 16 diary window, the interval can be extended up to 7 additional days, one at a time, to obtain the most recent 4 non-missing values. The assessment of whether 4 non-missing values exist in the Week 16 diary window, and subsequent extension of that window, does not consider censored data in window construction (i.e., they are counted as non-missing unless they are truly unobserved). If the Week 16 diary window has less than 4 non-missing values after extending the Week 16 diary window up to a maximum of 14 days, the Week 16 diary window is defined as 7 days and the mean of the window is missing.

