6.4. Handling of Dropouts or Missing Data

Intercurrent events (ICH E9 R1) are events which occur after the treatment initiation and make it impossible to measure a variable or influence how it would be interpreted.

Depending on the estimand being addressed, different methods will be used to handle missing data as a result of intercurrent events. Intercurrent events can occur through the following:

- application of one of the censoring rules (including after permanent study drug discontinuation or after rescue therapy)
- discontinuation
- missing an intermediate visit prior to discontinuation or rescue
- lost to follow-up.

Non-censor intercurrent events are events that are not due to the application of any censoring rule, i.e., the last 3 items in the list above.

Note that as efficacy and health outcome data can accrue after a patient permanently discontinues study drug or begins rescue therapy, specific general censoring rules to the data will be applied to all efficacy and health outcome observations subsequent to these events depending on the estimand being addressed. These specific censoring rules are described below.

The *primary censoring rule* will censor efficacy and health outcome data after permanent study drug discontinuation or after rescue therapy. This censoring rule will be applied to all continuous and categorical efficacy and health outcome endpoints. This censoring rule is equivalent to using all the data up to rescue.

A *secondary censoring rule* will only censor efficacy and health outcome data after permanent study drug discontinuation. This sensitivity analysis will include all observed values up to study drug discontinuation. The secondary censoring rule will be applied to primary and key secondary efficacy and health outcome endpoints as sensitivity analyses.

[Table JAHM.6.1](#) describes the planned imputation methods for efficacy and health outcome endpoints with associated censoring rules. Sections [6.4.1](#) through [6.4.5](#) summarize the methodology of each imputation rule.

Table JAHM.6.1. Imputation Techniques for Various Variables

Efficacy and Health Outcome Endpoints	Imputation Method
IGA(0,1), EASI75, 4-point Itch NRS improvement, EASI90, SCORAD75	NRI ^{ab} , pMI ^a , Tipping point ^a
EASI percent change, ADSS Item 2 change, Skin Pain NRS change	MMRM ^{ab} , mLOCF ^a , pMI ^a
All remaining categorical measures	NRI ^a
All remaining continuous efficacy and health outcome measures	MMRM ^a , mLOCF ^a

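### Section 6.14.1 ties exposure to the second last visit for every Lost to Follow-up patient, even when the last dose date is known, so off-drug days can be counted as exposure

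*SAP*

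**What the plan says.** SAP Section 6.14.1 gives the general rule as "date of last dose of study drug including rescue – date of first dose of study drug + 1", and dates the last dose as follows: "Last dose of study drug including rescue is calculated as last date on study drug". The exception comes next and opens with the words "For patients discontinuing study drug or study due to the reason 'Lost to Follow-up', the duration of exposure is calculated as". The formula it then gives for these patients is "date of second last visit - date of first dose of study drug + 1". The SAP does not define which visit is the second last.

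Four other sections bear on the point:

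- Section 6.4 notes that "efficacy and health outcome data can accrue after a patient permanently discontinues study drug or begins rescue therapy", so a patient may remain in the study off drug.
- Section 6.7 tabulates study discontinuation and treatment discontinuation separately, each with its own reason.
- Section 5.1 provides for off-drug follow-up until about 28 days past the final dose.
- Section 6.9 computes the dosing interval for compliance from the first and last dose dates, with no exception for patients lost to follow-up.

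**The concern.** A visit-based end date is a reasonable stand-in when a patient disappears on drug and nobody knows when dosing stopped. As written, though, the exception depends only on the discontinuation reason. It displaces a last dose date that is on file, and because it includes loss from the study it reaches patients whose dosing ended earlier for an unrelated reason. For them the second last visit says nothing about when dosing stopped.

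Total patient-years, the descriptive statistics for days of exposure and the 28-day exposure bands are at stake. The same patient can also have one dosing interval for compliance and a different one for exposure. Because the visit is undefined, two programmers could derive exposures one visit interval apart.

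**Working it through.** The SAP states no exposure figure, so there is nothing to reproduce. The check applies the two formulas of Section 6.14.1 to nominal visit dates.

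**Inputs.** Post-baseline visits are at Weeks 1, 2, 4, 8, 12 and 16 (Section 6.2.2). With first dose on Day 1, study day = 7 × week + 1, which gives Days 8, 15, 29, 57, 85 and 113. Exposure to any date (date − first dose date + 1) equals the study day of that date.

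**Two readings of the last visit.** Under A it is the last visit attended, so the second last visit is the one before it. Under B it is the record at which the loss is entered, so the second last visit is the last one attended.

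| Patient recorded as Lost to Follow-up | True days | Rule, A | Rule, B |
|---|---|---|---|
| Last dose Day 20, last seen Week 12 | 20 | 57 (+37) | 85 (+65) |
| Last dose Day 14, last seen Week 12 | 14 | 57 (+43) | 85 (+71) |
| Last dose Day 28, last seen Week 12 | 28 | 57 (+29) | 85 (+57) |
| Last dose Day 28, last seen Week 8 | 28 | 29 (+1) | 57 (+29) |
| Last dose Day 28, early termination visit Day 29, then lost | 28 | 15 (−13) | 29 (+1) |
| Last dose Day 56, early termination visit Day 57, then lost | 56 | 29 (−27) | 57 (+1) |
| Completer, last dose Day 112, lost in follow-up | 112 | 85 (−27) | 113 (+1) |
| On drug at Week 8 visit, never returns | at least 57 | 29 (at least −28) | 57 |

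**Bands.** The Day 20 patient belongs in the lowest band (under 28 days). The rule moves that patient up two bands under A (56 to under 84) and three under B (84 to under 112). The completer drops from 112 or more to 84 to under 112 under A and does not move under B.

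**Arm level.** A 120-patient arm with full exposure has 120 × 112 / 365.25 = 36.8 patient-years. One 27-day error is 27 / 365.25 = 0.074 patient-years, or 0.074 / 36.8 = 0.2%. The SAP gives no rate of loss. If 5% of the arm were affected, all in the same direction (an assumption), a 27-day error gives 0.05 × 27 / 112 = 1.2% and a 37-day error gives 0.05 × 37 / 112 = 1.7%. The 65-day error in the first row would give 0.05 × 65 / 112 = 2.9%, but only if all of that 5% were very early stoppers who stayed on until Week 12. Nothing in the SAP suggests that.

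**The case against.** A reader might infer that every completer lost in follow-up loses about four weeks, that early stoppers always gain time, and that every rate using exposure is wrong. The SAP does not support any of these.

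- **The completer loss needs two steps that the SAP does not settle.** First, the last visit must be the last attended one. Section 6.2.1 excludes from the safety population patients who were Lost to Follow-up at the first post-baseline visit, and treats safety data on them as rare. That suggests the loss is entered as a disposition record without assessments, which is reading B, and the completer then loses nothing. The patient last seen at Week 8 is also counted up to that visit. Second, loss during follow-up must count as discontinuing the study. Section 6.7 reports failure to complete follow-up alongside study discontinuation and leaves this open.
- **Early stoppers do not always gain.** One who has an early termination visit the day after the last dose and is then lost is cut by 13 or 27 days under A and is off by one day under B.
- **The reach is narrow.** The incidence rate in Section 6.14.2 uses observation time ending at the event or the last observation date, so it is unaffected. Categorical safety comparisons use Fisher's exact test on proportions. No efficacy result depends on the rule.
- **Intent.** The SAP does not say that the exception was meant only for unknown last doses; that is an inference.

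All of this stands and limits the point. It does not remove the early stopper with a known last dose who stays in the study off drug and is lost later. The Day 20 patient is given substantial off-drug time under both readings.

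**Conclusion.** The rule is wrong as written, with small impact. It overrides a known last dose date and can count off-drug days as exposure, by 37 or 65 days for a patient who stops on Day 20 and is last seen at Week 12. It also departs from the dosing interval in Section 6.9. That conclusion does not depend on how the second last visit is read. The cut for a Week 16 completer, from about 112 to 85 days, is conditional on both steps above and should not be stated as fact.

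The damage is limited to the descriptive exposure tables and total patient-years: about 0.2% of a 120-patient arm per 27-day error, and roughly 1 to 2% if 5% were affected in the same direction by errors of 27 to 37 days. The 5% is an assumption, and errors of opposite sign would partly cancel. The herpes simplex exposure-adjusted incidence rate in Section 6.14.5.6 may also be touched, but its denominator is not defined. The figures use nominal visit days.

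**What to change.** Reword the exception in Section 6.14.1 so that:

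1. the recorded last dose date is used whenever it is known, whatever the discontinuation reason, as the compliance formula in Section 6.9 does;
2. a visit-based substitute applies only when the last dose date is unknown because the patient was lost while on drug;
3. the visit meant is stated to be the last one the patient attended.

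The cost is a sentence or two of SAP text and a small programming change. No analysis is lost.
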